6.2.2 Screening and run-in period

Screening Period

No trial procedures should be done unless the patient has consented to taking part in the trial. Once informed consent is obtained, the patient is considered to be enrolled in the trial and have started screening. The patient should be recorded on the enrolment log and be registered in the IRT system as a screened patient before any other activities are performed. Patients who do not start the run-in period should be registered as a screen failure in the IRT system. Patients who do not fulfil all eligibility criteria for a reason that later resolves and allows eligibility criteria to be met, may be re-screened after discussion with the sponsor. Re-screening will only be allowed once.

The footnotes to the [flow chart](#) provide details about when screening procedures may be repeated and when re-screening is allowed.

Run-in Period

The run-in period for this trial lasts for two weeks prior to randomisation. During this period the patient will start to collect their UACR samples as described in the [flow chart](#) and in [section 5.1.1](#).

6.2.3 Treatment period

The treatment period in this trial is 20 weeks. All visit procedures should be completed as indicated in the [flow chart](#).

6.2.4 Early discontinuation of Treatment

Patients who discontinue treatment prematurely and who do not withdraw their informed consent should return for an End of Treatment visit.

If the patient has stopped taking trial drug the day of a scheduled visit or one day prior, the scheduled visit should be performed as an EoT Visit. All samples including PK and all biomarkers (██████, UACR and others) should be collected in addition to safety samples. If the early discontinuation does not coincide with a scheduled visit, the patient should return for an EoT Visit. PK or biomarker samples should not be collected, but all safety assessments must be performed as indicated in the [flow chart](#).

The patient should be encouraged to complete all visits and procedures in the FUp period (see [section 6.2.5](#)). If the patient does not wish to complete all visits or procedures, they should have FUp1 as a minimum.

6.2.5 Follow-up period and trial completion

The Follow-up Period consists of three visits, FUp1, FUp2 and FUp3 with a timepoint for UACR and [REDACTED] [REDACTED] in between these visits, please see the [flow chart](#) for timelines and visit details.

The Residual Effect Period (REP) in this study is 7 days, visit FUp1 should therefore be performed no earlier than 7 days after the End of Treatment Visit. FUp visits FUp2 and FUp3 should also be scheduled relative to the EoT Visit, i.e. FUp2 will be 2 weeks after EoT, 3 weeks after EoT there will be home sampling without visit, and FUp 3 should be 4 weeks after EoT.

Visit FUp3 may be conducted as a Home visit where permitted (see [section 6.2.1](#)), however should a patient have any adverse event(s) that require assessment then the Investigator may request they attend the site for a full assessment.

Participation in this trial is concluded once FUp3 has been completed.

7. STATISTICAL METHODS AND DETERMINATION OF SAMPLE SIZE

This is a Phase II, randomised, double-blind (within dose groups), placebo-controlled and parallel group trial to investigate the effect of different doses of BI 685509 on UACR reduction over 20 weeks in patients with diabetic kidney disease.

The primary endpoint for patients is Change from baseline in log transformed UACR measured in 10-hour urine after 20 weeks of trial treatment. The purpose of this trial is to demonstrate PoC (proof of concept) of clinical activity of BI 685509 on the primary endpoint and to determine the optimal dose for phase III. The methodology for dose finding employing both multiple comparison procedures and modelling techniques (MCPMod) will be applied to the 4 groups of patients, i.e. the patients on BI 685509 in each of the three dose groups and the combined patients from all dose groups who are not on BI 685509.

7.1 NULL AND ALTERNATIVE HYPOTHESES

The null hypothesis is that there is a flat dose response curve for Change from baseline in log transformed UACR measured in 10-hour urine after 20 weeks of trial treatment comparing the placebo and the BI 685509 dose groups whereas the alternative hypothesis is that, there is a non-flat dose response curve indicating a benefit of BI 685509 in at least one of the patient groups.

The MCPMod procedure allows for simultaneous evaluation of different potential dose response patterns, whilst protecting the overall probability of Type I error (one-sided α of 5 %). The pre-specified models and their parameters used for this test are outlined in [section 7.2.1](#).

7.2 PLANNED ANALYSES

7.2.1 General considerations

The following analysis sets will be defined for statistical analyses:

Entered Set (ES): This patient set includes all patients who signed informed consent. The ES will be used for the analysis of patient desposition.

Randomised Set (RS): This patient set includes all entered and randomised patients. The RS will be used for the analyses of protocol deviations as well as demographics and baseline characteristics.

Treated Set (TS): This patient set includes all patients who received at least one dose of study medication. The TS is used for safety analyses and exposure.

Full Analysis Set (FAS): The patient set includes all patients who had at least one baseline measurement of UACR in week -2, -1, or 0 and at least one post-baseline measurement after week 6. The FAS is the main analysis set for the analysis of efficacy.

The pharmacokinetic set (PKS): This patient set includes all patients in the TS who provide at least one PK parameter that was not excluded because of protocol deviations relevant to the statistical evaluation of PK endpoints as defined in [section 5.3](#).

Further Analysis Sets will be defined in the TSAP, if needed.

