7.2.2 Primary endpoint analyses

The primary objectives are to demonstrate a non-flat dose response curve, evaluate the quantitative treatment effect size, and evaluate the dose-response relationship. The primary analysis will be performed on the FAS.

For the proof of concept (PoC) and dose finding, both multiple comparison procedures and modelling techniques (MCPMod) will be applied. The primary estimand of interest is the treatment effect using a primary approach. In the primary approach, trial medication is assumed to be taken as randomised and an intercurrent event is defined as an event of treatment discontinuation, death, or dropin/dropout of SGLT2i. The primary approach for primary analysis will include all data prior to intercurrent event. Any data collected after the intercurrent event will not be included in the primary analysis. The resulting missing data will be assumed to be missing at random (MAR).

The three different approaches for handling ICEs are summarized in the [Table 7.2.2: 1](#) below.

Table 7.2.2: 1 Summary of strategies for handling ICEs

Estimand strategy name	Treatment	ICE handling
Primary approach	Randomised treatment	Study med d/c: include data prior to study med d/c. Death: include data prior to death. SGLT2i initiation/discontinuation: include data prior to SGLT2i start/stop.

Table 7.2.2: 1 Summary of strategies for handling ICEs cont.

Estimand strategy name	Treatment	ICE handling
[REDACTED]	[REDACTED]	[REDACTED]
[REDACTED]	[REDACTED]	[REDACTED]

Treatment effect

The primary analysis will first address a dose relationship between doses of BI 685509 and placebo. The analysis will include the fixed, categorical effect of treatment at each visit, and the fixed continuous effects of baseline log transformed UACR at each visit. Visit will be treated as the repeated measure with an unstructured covariance structure used to model the within-patient measurements.

To conduct multiple comparison in MCPMod across doses, covariate adjusted fixed effect estimates of average response for each dose group and the covariance matrix will be extracted from the fit by the following MMRM and used for MCPMod analysis.

Statistical model (MMRM):

$$y_{ijklm} = \beta_j U_i + \tau_{jk} + \eta_l + \psi_m + e_{ij},$$

where

$$e_{ij} \sim N(0, \Sigma),$$

y_{ijkm} = reduction in log transformed UACR at visit j from baseline for subject i in stratum m ($m=1,2$) receiving treatment k ($k=1,\dots,4$),

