6.6.2 Efficacy data

6.6.2.1 Primary endpoint

Missing data for primary analysis will not be imputed:

- If some UACR value(s) for UACR at baseline is (/are) missing, all available UACR samples in week -2, -1, and 0 will be used to derive UACR at baseline.
- If any UACR value after randomisation is missing, the missing UACR will not be imputed; missing UACR due to ICEs will not be imputed.

The Mixed-effect Model for Repeated Measures (MMRM) approach used for the primary analysis (see [Section 7.4.1](#)) allows for missing data, assuming the missing data mechanism is ignorable. Even patients with only one post-baseline assessment can be included in the model and can, therefore, participate in variance estimation. The statistical model assumes that patients who had an ICE would have behaved similarly to those who remained in the study. The table below describes how/when to derive UACR values for MMRM:

Table 6.6.2.1: 1 Principal rule of UACR derivation for MMRM

UACRs for MMRM	UACR at baseline	UACR at visit 6	UACR at visit 7	UACR at EoT
Visits need to be included	First Morning Void (FMV) or 10-hour urine UACR baseline is defined as the mean of all non-missing assessments from Visit 2 until prior to the first intake of trial medication.	All available scheduled visits at visit 6	All available scheduled visits at visit 7	All available scheduled visits between visit 8 and EoT
Derivation	Average of all available UACR measurements defined at each visit			

Note: all available/scheduled UACR measurements will be used: no imputation for missing UACR measurement; this rule will be applied to FMV and 10-hour urine samples, respectively.

Sensitivity analyses will be conducted to investigate the potential effect of ICE handling approaches on the results of the primary analysis. Details about implementation of the sensitivity statistical analyses are described in [Section 7.4](#).

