7.4 PRIMARY ENDPOINT(S)

7.4.1 Primary analysis of the primary endpoint(s)

The primary endpoint will be analysed in combination with the primary approach of handling ICEs (see [Section 5.1](#)). The FAS is the main analysis set for the analysis of efficacy: the patient set includes all patients who had at least one baseline measurement of 10 hour UACR in week -2, -1, or 0 and at least one post-baseline measurement after week 6.

Refer to Section 7.2.2 of the CTP for a description of the statistical analysis for the change from baseline in log transformed UACR measured in 10-hour urine at 20 weeks of trial treatment.

The adjusted mean reduction in log transformed UACR in 10-hour urine from baseline at 20 weeks and its standard deviation will be obtained from MMRM for the placebo and treatment groups. For the MMRM model, derived UACRs at baseline, visit 6, visit 7, and EoT, which were described in [Section 6.6.2.1](#), will be used.

SAS code for **the MMRM model** will be based on the following structure:

```
PROC MIXED DATA=alldat cl method=reml;

CLASS visit trt subject;

MODEL chg = base*visit visit*trt typediabetes SGLT2ibase / ddfm=kr s CL;
REPEATED visit / subject= subject type=un r rcorr;

LSMEANS visit*trt / pdiff=all om cl alpha=0.05 slice=visit;

RUN;
```

In the event of model non-convergence, the methods described in [Section 10.1](#) will be attempted (in order) to overcome it.

Multiple Comparisons Procedure - Modelling (MCP-Mod) Analysis

For the primary analysis, the dose-response relationship will be modelled using the total daily doses: 3 mg, 6 mg, and 9 mg. The multiple comparison procedure will then be implemented using optimal contrast tests which control the family-wise type I error rate at a one-sided $\alpha = 0.05$. For the MCPMod test, the optimal contrasts of each candidate model are calculated using the R-function optCont.

For the final evaluation, the contrast will be provided using the expected model means from the candidate set and the estimated variance-covariance matrix extracted from the MMRM model.

Once the significance of a dose-response signal is established, the dose-response profile and the target dose can be estimated using a model averaging approach for significant models.

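### The FAS needs a UACR after week 6, so a treated patient whose only usable model value is Visit 6 (week 6) and who gives no later urine is left out of the primary analysis

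*Protocol*

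**What the plan says.** **Analysis set.** Protocol 7.2.1 requires "at least one baseline measurement of UACR in week -2, -1, or 0 and at least one post-baseline measurement after week 6". SAP 7.4.1 ties the baseline part to 10-hour UACR and keeps "at least one post-baseline measurement after week 6". Protocol 7.2.2 runs the primary analysis on this set.

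**Model.** SAP 7.4.1: "For the MMRM model, derived UACRs at baseline, visit 6, visit 7, and EoT". Table 6.6.2.1:1 confirms that the three post-baseline responses are Visit 6, Visit 7 and EoT (the average from Visit 8 to EoT). SAP 6.6.2.1 adds: "Even patients with only one post-baseline assessment can be included in the model and can, therefore, participate in variance estimation".

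**Intercurrent events.** Protocol 7.2.2: "The primary approach for primary analysis will include all data prior to intercurrent event", and "Any data collected after the intercurrent event will not be included in the primary analysis". What is then missing is assumed missing at random (MAR).

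**Sampling after early discontinuation.** Protocol 6.2.4 counts UACR among the biomarkers. For an EoT visit that does not coincide with a scheduled visit it says "PK or biomarker samples should not be collected, but all safety assessments must be performed". Follow-up is encouraged, but "If the patient does not wish to complete all visits or procedures, they should have FUp1 as a minimum". FUp1 is a telephone contact (Protocol 3.1), and the UACR and eGFR sampling flow chart has no urine collection for it.

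**The concern.** The model uses a Visit 6 value, but that value does not by itself place the patient in the model's analysis set. Protocol 7.2.2 promises all data before the intercurrent event. The FAS rule withholds some of it, for the patients who leave soonest after Visit 6.

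Under MAR, an MMRM is protected against selective dropout because it conditions on what leavers showed before they left. If those who leave after Visit 6 responded differently at Visit 6, and leave at different rates by dose, deleting their values biases the week-20 dose-group differences. These differences feed the MCPMod analysis and the 0.22 proof-of-concept threshold. The bias can go either way: it flatters the drug if poor responders leave the active arm, and penalises it if good responders do.

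The condition also does not require the later measurement to be on treatment. Whether a valid Visit 6 value is used can therefore depend on whether the patient later supplies off-treatment urine, which the primary approach itself discards.

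**Working it through.** **1. Timing.** Visit 6 is Day 43 (week 6), window ±2 days. The sampling chart puts urine collection 2 and 1 days before the visit.
- Visit on Day 43: samples on Days 41 and 42.
- Visit on Day 41: samples on Days 39 and 40.
- Visit on Day 45: samples on Days 43 and 44.

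Only a late Visit 6 could yield a sample that is literally after week 6. The next on-treatment response in the model is Visit 7, at week 12.

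**2. Who falls where.**

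| Patient | In FAS as written? | Usable pre-event MMRM value? |
|---|---|---|
| Stops between Visits 6 and 7, no later urine | No | Yes (Visit 6) |
| Same, but gives 10-hour urine at FUp2 or FUp3 | Yes | Yes (Visit 6) |
| Stops after Visit 7 | Yes | Yes |
| Stops at week 4, gives FUp3 urine at week 4 + 4 = 8 | Yes | No |

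The first two rows differ only in off-treatment behaviour.

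**3. The SD, from the stated power.** Protocol 7.5 gives 88.5% power with 60 per group, one-sided 5%, and effects of 0, 0.10, 0.20 and 0.35, but no SD. The figure therefore cannot be reproduced directly. A maximum-contrast test with the five stated candidate shapes (critical value about 1.90) gives power of 91.0% at SD 0.65, 87.0% at 0.70 and 88.5% at about 0.68. SD 0.68 is used below as an assumption.

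**4. Bias.** Assumptions: equal SD σ = 0.68 at Visit 6, Visit 7 and EoT; equal correlation ρ of 0.5 or 0.7 between visits; and a true 9 mg effect of 0.35. Stopping after Visit 6 is logistic in the standardised Visit 6 residual z, with slope β and mean rate p̄. If nobody lost gives later urine, the Visit 6 mean of those kept shifts in each arm by

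β · E[p(1−p)] / (1−p̄) SDs,

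and the bias in the week-20 difference is ρ · σ · (shift in 9 mg − shift in placebo).

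Worked case, β = 1, loss 5% placebo and 15% at 9 mg:
- placebo shift: 0.0448 / 0.95 = 0.0471
- 9 mg shift: 0.1127 / 0.85 = 0.1326
- bias at ρ = 0.5: 0.5 × 0.68 × 0.0855 = 0.029
- bias at ρ = 0.7: 0.7 × 0.68 × 0.0855 = 0.041

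If half give follow-up urine, the shift becomes 0.5 · β · E[p(1−p)] / (1 − 0.5p̄). Absolute bias, for ρ from 0.5 to 0.7:

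| Loss, placebo / 9 mg | β = 1, no later urine | β = 1, half give urine | β = 0.5, no later urine |
|---|---|---|---|
| 2% / 5% | 0.009–0.013 | 0.005–0.006 | 0.005–0.007 |
| 5% / 10% | 0.015–0.021 | 0.007–0.010 | 0.008–0.012 |
| 5% / 15% | 0.029–0.041 | 0.013–0.018 | 0.016–0.023 |

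A simulation with 1,000,000 patients per arm agrees. Keeping the Visit-6-only patients returned 0.348 to 0.352 throughout. Equal loss (5%/5% or 10%/10%) and random loss at 5%/15% gave bias below 0.001. A separate simulation at 60 per arm, with loss in the active arm only (5% or 10%), gave estimates of about 0.37 to 0.40 under moderate selection and 0.39 to 0.44 when the worst Visit 6 values left.

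**5. Effect on the PoC threshold.** The SE of the 9 mg difference is 0.68 × √(2/60) = 0.124. The chance that the observed difference reaches 0.22 is Φ((0.35 − 0.22)/0.124) = 85%. A bias of 0.02 moves it to Φ(0.11/0.124) = 81% or Φ(0.15/0.124) = 89%.

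**6. Precision, random loss.** With m of 60 per arm reaching week 20, the variance of an arm mean is proportional to (1−ρ²)/m + ρ²/60 if Visit-6-only patients are kept, and to 1/m if they are dropped.
- 5% loss (m = 57): SE 0.1266 (ρ = 0.5) or 0.1258 (ρ = 0.7) if kept, 0.1274 if dropped.
- 10% loss (m = 54): SE 0.1292 or 0.1276 if kept, 0.1309 if dropped.

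Dropping them raises the SE by 0.6% to 2.5%.

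**The case against.** The wording may be loose. The primary endpoint is described as measured after 20 weeks, although it averages urine from Visit 8 onward, so after week 6 might be meant to include the week-6 visit. A late Visit 6 sample could also qualify literally. This stands as a reason to ask what was intended, but a definition that supports two readings still needs correcting.

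The rule may be deliberate, since target dose is reached only at week 4 and two weeks at that dose is little. This does not hold up. Off-treatment follow-up urine satisfies the same condition, so the rule does not secure longer exposure, and the model itself uses Visit 6.

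The SAP sentence on one post-baseline assessment is a general remark about MMRM, and a patient with only a Visit 7 value satisfies both it and the FAS. That is fair: the sentence does not override the FAS, and the stronger conflict is with the promise to use all pre-event data. That promise could be read as applying only within the FAS, but the Visit 6 values would still be lost.

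The group is narrow. Protocol 3.3.4 asks sites to make every effort to obtain UACR, and FUp2 and FUp3 include it. Every loss rate above is assumed, and the largest figure needs 9 of 60 patients lost from one arm in a six-week interval. All of this stands and limits the size. The week-4 stopper with FUp3 urine adds no response to the primary model, so that mismatch affects only the denominator.

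**Conclusion.** The FAS as written is inconsistent with the primary model and with the primary intercurrent-event strategy. It excludes a reachable group of treated patients with valid pre-event data. The likely effect is modest: with loss of 5% on placebo and 10% on 9 mg, the bias is roughly 0.007 to 0.021 log units at a log-odds of 1 per SD, depending on correlation and on how many give follow-up urine. That compares with an SE of 0.124 and a threshold of 0.22. It reaches 0.041 in the upper scenario of the main table, and more if selection is stronger and confined to the active arm. If loss is random or equal across arms, only a little precision is lost. These figures rest on a back-solved SD and on assumed correlations, loss rates and selection strength. The simulations also assume that loss is MAR given Visit 6. An effect on MCPMod power or type I error was not quantified. The inconsistency itself needs none of these assumptions and should be corrected.

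**What to change.** In Protocol 7.2.1 and SAP 7.4.1, define the FAS for the primary approach as randomised and treated patients with at least one baseline 10-hour UACR and at least one post-baseline 10-hour UACR eligible for the MMRM (Visit 6, Visit 7 or EoT) before any intercurrent event. Membership should follow the nominal or assigned visit, not the calendar day.

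Use the same set for Supplementary 2, which is also limited to pre-event data. For Supplementary 1, drop the pre-event restriction. If Supplementary 1 is run on the current FAS, it will not recover the excluded patients. Keep the current set as a sensitivity analysis.

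If from week 6 onward was what the authors meant, saying so admits the Visit 6 patients. The pre-event condition would still be needed to keep out patients with no usable model value.

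The cost is one definition in two documents, with a line on how it applies to each supplementary approach, plus one rerun on the current set. No new data are needed, and the MMRM and its visits do not change. The change should be made before unblinding.

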7.2.2 Primary endpoint analyses

The primary objectives are to demonstrate a non-flat dose response curve, evaluate the quantitative treatment effect size, and evaluate the dose-response relationship. The primary analysis will be performed on the FAS.

For the proof of concept (PoC) and dose finding, both multiple comparison procedures and modelling techniques (MCPMod) will be applied. The primary estimand of interest is the treatment effect using a primary approach. In the primary approach, trial medication is assumed to be taken as randomised and an intercurrent event is defined as an event of treatment discontinuation, death, or dropin/dropout of SGLT2i. The primary approach for primary analysis will include all data prior to intercurrent event. Any data collected after the intercurrent event will not be included in the primary analysis. The resulting missing data will be assumed to be missing at random (MAR).

The three different approaches for handling ICEs are summarized in the [Table 7.2.2: 1](#) below.

Table 7.2.2: 1 Summary of strategies for handling ICEs

Estimand strategy name	Treatment	ICE handling
Primary approach	Randomised treatment	Study med d/c: include data prior to study med d/c. Death: include data prior to death. SGLT2i initiation/discontinuation: include data prior to SGLT2i start/stop.

Table 7.2.2: 1 Summary of strategies for handling ICEs cont.

Estimand strategy name	Treatment	ICE handling
[REDACTED]	[REDACTED]	[REDACTED]
[REDACTED]	[REDACTED]	[REDACTED]

Treatment effect

The primary analysis will first address a dose relationship between doses of BI 685509 and placebo. The analysis will include the fixed, categorical effect of treatment at each visit, and the fixed continuous effects of baseline log transformed UACR at each visit. Visit will be treated as the repeated measure with an unstructured covariance structure used to model the within-patient measurements.

To conduct multiple comparison in MCPMod across doses, covariate adjusted fixed effect estimates of average response for each dose group and the covariance matrix will be extracted from the fit by the following MMRM and used for MCPMod analysis.

Statistical model (MMRM):

$$y_{ijklm} = \beta_j U_i + \tau_{jk} + \eta_l + \psi_m + e_{ij},$$

where

$$e_{ij} \sim N(0, \Sigma),$$

y_{ijkm} = reduction in log transformed UACR at visit j from baseline for subject i in stratum m ($m=1,2$) receiving treatment k ($k=1,\dots,4$),

U_i = the baseline* measurement of log-transformed UACR of subject i ,

β_j = coefficient of baseline effect at visit j ,

τ_{jk} = the effect of treatment k at visit j ,

η_l = the effect of stratum l for type of diabetes mellitus,

ψ_m = the effect of stratum m for SGLT2i use at randomisation,

e_{ij} = the random error associated with the j th visit of the i th subject. Errors are independent between subjects,

Σ = an unstructured covariance matrix.

* baseline is defined as the mean of all non-missing assessments from Visit 2 until prior to the first intake of trial medication.

A non-flat dose-response relationship is established if for primary endpoint, the null hypothesis of no dose effect (i.e., a flat dose response curve) is rejected for at least one of the pre-specified models with respect to the one-sided type I error at 5%. PoC is established if for the primary endpoint, at least $\geq 20\%$ mean reduction in UACR at least in one BI 685509 dose

group (0.22 difference in mean log transformed UACR) compared to placebo. For PoC, patients will be analyzed as randomised, according to the primary approach in [Table 7.2.2: 1](#).

The same process will be repeated for the supplemental 1 and 2 approaches in [Table 7.2.2: 1](#).

Dose finding

The second primary objective is to determine therapeutic dose. The trial will characterize the dose-response curve for BI 685509 in patients with diabetic kidney disease (DKD) by assessing 3 doses and placebo. The response is the change from baseline in log transformed UACR measured in 10-hour urine after 20 weeks of trial treatment. Patients will be evaluated in the dose group they were assigned to at randomisation for primary analysis in the MCPMod analysis.

The analyses for dose-finding will be performed using MCPMod whereby several possible dose response models (patterns) will be evaluated to identify the best-fitting model or subset of models (refer to [Figure 7.5: 1](#)). If PoC is established, the statistically significant (best fitting) model(s) from the candidate set are refitted to the data to generate new estimates for all model parameters from the data. The final model will be obtained via model averaging across the significant models based on Akaike Information Criterion (AIC). The target dose(s) can be estimated from that model by incorporating information on the minimum clinically relevant effect and accounting for safety. Doses within the dose range investigated (0 to 9 mg, total daily dose) will be considered.

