7.5 DETERMINATION OF SAMPLE SIZE

The sample size calculation is conducted assuming effect size of BI 685509 versus placebo, (0, 0.10, 0.20, 0.35) for (placebo, BI 685509 3 mg, BI 685509 6 mg, BI 685509 9 mg total daily dose) in log transformed UACR measured in 10-hour urine after 20 weeks of trial treatment from baseline. The pre-specified models in [Figure 7.5: 1](#) are used for testing null hypothesis. The following models have been selected as the candidate set of possible dose response patterns based on current expectation. Assuming the following dose groups will be tested: placebo, active BI 685509 3 mg, 6 mg, and 9 mg in terms of total daily dose.

Emax: 80% of the maximum effect is achieved at 6 mg.

Exponential: 20% of the maximum effect is achieved at 3 mg.

Linear: No assumption is needed.

Quadratic: 50 % of the maximum effect is achieved at a dose of 3 mg.

90 % of the maximum effect is achieved at a dose of 6 mg.

Sigmoid emax: 30 % of the maximum effect is achieved at a dose of 3 mg.

90 % of the maximum effect is achieved at a dose of 6 mg.

[figure not shown]

Figure 7.5: 1 Shape of the considered dose response patterns for the MCPMod analysis (dose reflects planned daily dose)

In a scenario with assumed effect of (0, 0.10, 0.20, 0.35) in log (UACR) change from baseline to week 16 for (placebo, BI 685509 3 mg, BI 685509 6 mg, BI 685509 9 mg total daily dose), 88.5% of statistical power considering one-sided 5% alpha was achieved with sample size per treatment from 60. The sample size/power calculation were determined based on 10,000 simulations for the scenario using R3.6.1.

8. INFORMED CONSENT, TRIAL RECORDS, DATA PROTECTION, PUBLICATION POLICY, AND ADMINISTRATIVE STRUCTURE

The trial will be carried out in compliance with the protocol, the ethical principles laid down in the Declaration of Helsinki, in accordance with the ICH Harmonized Guideline for Good Clinical Practice (GCP), relevant BI Standard Operating Procedures (SOPs), the EU directive 2001/20/EC / EU regulation 536/2014, the Japanese GCP regulations (Ministry of Health and Welfare Ordinance No. 28, March 27, 1997) and other relevant regulations. Investigators and site staff must adhere to these principles. Deviation from the protocol, the principles of ICH GCP or applicable regulations as will be treated as “protocol deviation”.

Standard medical care (prophylactic, diagnostic and therapeutic procedures) remains the responsibility of the treating physician of the patient.

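### Proof of concept is worded as a point-estimate rule that does not require the MCPMod test to be significant, and the protocol and SAP open dose finding on different conditions

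*Protocol*

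**What the plan says.** Protocol section 7 gives the aim: "The purpose of this trial is to demonstrate PoC (proof of concept) of clinical activity of BI 685509 on the primary endpoint". Section 7.2.2 then sets two rules in consecutive sentences.

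- **Non-flat dose response:** established if the flat-curve null hypothesis "is rejected for at least one of the pre-specified models with respect to the one-sided type I error at 5" per cent.
- **PoC:** established by at least a 20% "mean reduction in UACR at least in one BI 685509 dose" group, with the threshold given on the log scale as "0.22 difference in mean log transformed UACR) compared to placebo". No test, confidence bound or significance level is attached.

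Earlier in the same section the methods are linked: "For the proof of concept (PoC) and dose finding, both multiple comparison procedures and modelling techniques (MCPMod) will be applied".

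The gate to dose finding is worded in two ways.

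- **Protocol 7.2.2, Dose finding:** "If PoC is established, the statistically significant (best fitting) model(s) from the candidate set are refitted to the data".
- **SAP 7.4.1:** "Once the significance of a dose-response signal is established, the dose-response profile and the target dose can be estimated".

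The visible SAP text does not repeat the 20% condition. It refers to protocol 7.2.2 for the analysis, and SAP section 4 reports no change to the planned analysis.

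On power, protocol 7.5 reports "88.5% of statistical power considering one-sided 5% alpha was achieved with sample size per treatment from 60" for effects of 0, 0.10, 0.20 and 0.35, and says the candidate models are used to test the null hypothesis. The figure therefore describes the MCPMod test. No SD is given.

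**The concern.** Taken literally, PoC depends only on whether the largest of three observed differences reaches 0.22. A maximum of three noisy differences can do that by chance, and the plan does not say how often. PoC could then be declared in a trial whose dose-response test had failed. Protocol 7.2.2 would call for significant models to be refitted when there were none.

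The opposite case also matters. If the test is significant but no dose reaches 0.22, the protocol's gate is shut and the SAP's is open. This mismatch remains even if PoC is read as requiring both conditions.

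The protocol calls the trial's results crucial for the decision on further development, so the success rule should not have to be interpreted after unblinding.

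**Working it through.** **Inputs (protocol 7.2.2, 7.4, 7.5).** 60 patients per group, with placebo pooled as 3 × 20; one-sided 5%; threshold 0.22; effects (0, 0.10, 0.20, 0.35) at 0, 3, 6 and 9 mg; five candidate shapes. The SD is not stated and is an assumption throughout.

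**Candidate shapes, solved from the stated guesses.**
- Emax, d/(ED50 + d): 6/(ED50 + 6) = 0.80 gives ED50 = 1.5.
- Exponential, exp(d/δ) − 1: (exp(3/δ) − 1)/(exp(9/δ) − 1) = 0.20 gives δ = 6.73, taking 9 mg as the maximum.
- Linear: no parameter.
- Quadratic, d + δd²: δ = −0.0529, the mean of the solutions for 50% at 3 mg and 90% at 6 mg.
- Sigmoid Emax: h = ln(21)/ln(2) = 4.39; ED50 = 6/9^(1/h) = 3.64.

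**Test.** With equal groups, each optimal contrast c is the centred shape scaled to unit length. The statistic is T = c′ȳ / (s/√60) on 236 degrees of freedom, and the test uses the largest of the five. The simulated 5% critical value is about 1.91. Separate runs gave 1.908 to 1.914, which moves the percentages below by at most about 0.4 points.

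**Reproducing the plan's figure.** Without an SD, 88.5% cannot be reproduced from stated inputs. Solving backwards, SD = 0.68 gives 88.5% MCPMod power in the planning scenario.

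**Why the point rule is loose at that SD.** The standard error of a dose-minus-placebo difference is 0.68 × √(2/60) = 0.124. The threshold is 0.22/0.124 = 1.77 standard errors. One dose with no effect exceeds this with probability about 3.8%, and there are three chances sharing one placebo group.

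**Simulated trials at SD 0.68 (%).**

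| Outcome | Flat curve | Planning scenario |
|---|---|---|
| MCPMod significant | 5.0 | 88.5 |
| PoC as worded (largest difference ≥ 0.22) | 9.2 | 87.6 |
| Both | 4.1 | 85.4 |
| PoC as worded, not significant | 5.1 | 2.2 |
| Significant, PoC not met | 0.9 | 3.1 |

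Under a flat curve, 5.1/9.2 = 55% of PoC declarations would come with a non-significant test. The 3.1% is where the two gates differ. The 2.2% is where PoC is met with no significant model to refit.

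**Dependence on the SD (%).**

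| SD | MCPMod power | PoC as worded, flat | Both, flat | PoC without significance, flat |
|---|---|---|---|---|
| 0.50 | 98.8 | 2.1 | 1.5 | 0.6 |
| 0.60 | 94.4 | 5.6 | 3.2 | 2.4 |
| 0.68 | 88.5 | 9.2 | 4.1 | 5.1 |
| 0.80 | 78.0 | 15.1 | 4.7 | 10.4 |

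The point rule crosses 5% at an SD of about 0.585. The 0.80 row shows direction only, since its power does not fit the stated 88.5%. If 10% or 20% of patients are lost at SD 0.68 (54 or 48 per group), PoC as worded under a flat curve becomes 11.0% or 13.1%. That assumes the 88.5% contains no allowance for loss; section 7.5 does not mention one.

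**Rounding.** −ln(0.80) = 0.223. Using 0.223 in place of 0.22 changes 9.2% to 8.7% and 4.1% to 4.0%.

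**The case against.** The strongest reply is that a joint rule is intended. Section 7.2.2 applies MCPMod to PoC as well as dose finding, places the test sentence directly before the PoC sentence, and then speaks of refitting significant models, which presupposes that at least one exists. Under that reading false PoC is bounded by the stated 5% (4.1% here). The SAP defers to protocol 7.2.2, and its gate sentence is permissive, so its silence on 20% need not cancel the protocol's condition. A 20% threshold is also an ordinary go/no-go criterion, and no passage says PoC alone triggers further development.

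Much of this stands. The joint reading is plausible, and the text does not show that the sponsor would declare PoC on a failed test. False entry into dose finding is 4.1% under the protocol gate and 5.0% under the SAP gate, so alpha is protected there. The size also depends on the SD: the non-significant share of false PoC declarations is 2.4/5.6 = 43% at SD 0.60 and 0.6/2.1 = 29% at 0.50.

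The reply does not supply the missing condition. The protocol uses separate sentences to establish two different claims and never joins them. Under the joint reading, 88.5% is not the probability of PoC and the two gates still differ.

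**Conclusion.** The concern holds. As written, PoC is a point-estimate rule with no stated error rate or power, and the two documents word the gate to dose finding differently. At the SD implied by the protocol's own power figure, a flat dose response would meet PoC as worded in 9.2% of trials, against 4.1% if significance were also required. The gates differ in 3.1% of trials in the planning scenario.

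These figures assume an SD of 0.68, complete data, and raw group means in place of MMRM-adjusted means. At an SD below about 0.585 the point rule is stricter than 5%. The exposure is limited to the PoC declaration, so this should be fixed before unblinding but does not threaten the trial's design.

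**What to change.** Before unblinding:

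1. State in protocol 7.2.2 and SAP 7.4.1 that PoC requires both (i) at least one MCPMod contrast significant at the multiplicity-adjusted one-sided 5% level and (ii) an MMRM-adjusted, placebo-corrected UACR reduction of at least 20% (0.22 log units) at week 20 in at least one dose.
2. Use that same condition as the gate to dose estimation in both documents.
3. State the SD assumed in protocol 7.5, and report the joint probability of meeting both conditions (about 85% at SD 0.68) beside the 88.5%.

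The cost is wording. In the planning scenario the probability of meeting PoC falls from 87.6% as worded to 85.4%, which is 2.2 points; the reported joint figure is 88.5 − 85.4 = 3.1 points below the MCPMod power.
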